### 4.2 Phase I/II Study Design and Duration

This is a non-randomized, single-arm, multicenter, phase I/II study in adult patients with ED-SCLC, who achieved stable disease, partial response, or complete response after completion of platinum-based first-line chemotherapy. Fifty participants will be enrolled to receive thoracic radiation therapy (30 Gy in 10 fractions) followed by nivolumab/ipilimumab combination therapy for 4 cycles and then maintenance nivolumab until progression. The study design schematic is presented in Figure 4.2-1.

**Figure 4.2-1.** Study Schematic

The treatment regimen is as follows:

At least 3 weeks, but not longer than 8 weeks after completion of systemic chemotherapy, patients will initiate thoracic radiation therapy targeting the initially involved supraclavicular, hilar and mediastinal lymph node stations as well any other residual intrathoracic disease seen on restaging CT or PET-CT after completion of systemic therapy. Details of the Radiotherapy Treatment Schedule are outlined in Table 5.2-1. At least 14 days and not more than 21 days after completion of RT, patients will commence nivolumab 1 mg/kg (30-minute IV infusion) and ipilimumab 3 mg/kg (90-minute IV infusion) every 3 weeks for 4 doses, followed by nivolumab 480 mg every 4 weeks, as described in Table 6.5-1.

The detailed 3-part schedule of investigational treatments is as follows:

- 1)** Monday to Friday: thoracic radiation therapy at a dose of 3 Gy daily for 10 treatments
- 2)** After at least 14 days but not more than 21 days, initiate combined nivolumab 1 mg/kg + ipilimumab 3 mg/kg every 3 weeks for 4 doses;
- 3)** After part 2 of treatment, initiate maintenance nivolumab at least 42 days but not more than 56 days, delivered every 4 weeks at a dose of 480 mg/cycle.

Patients will undergo ongoing 4-week cycles until discontinuation criteria are met (Section 4.6). The full study schedule calendar is outlined in Appendix 1.

On-study tumor assessments commence 4 weeks after initiation of thoracic radiation therapy and will be conducted according to the study calendar schedule(+/-5 days) for the first 33 weeks. After week 36, radiographic tumor assessments will be performed every 12 weeks (+/-5 days) until disease progression (See Tables 7.4-1 and 7.4-2).

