#### **4.2.1 Study Phases**

The study is divided into the following phases: Screening, Treatment, and Follow-up.

The study calendar is outlined in Appendix 1.

**1. Screening:** Screening begins after the participant signs the informed consent form (ICF) and is enrolled on the study through the Moffitt Clinical Research Network (MCRN) at Moffitt Cancer Center.

- Whenever possible, tumor tissue (archival or recent tumor biopsy 10 slides or tissue block) should be submitted to the central lab for correlative studies. Participants must consent to allow the acquisition of tumor tissue by study personnel for performance of the correlative studies.
- Baseline assessments must be performed within the timeframes described in Table 7.1-1.
- For patients with known brain metastases at presentation, brain radiotherapy (whole brain radiation therapy (WBRT) or stereotactic radiation) may be offered, per local standard of care. Patients with asymptomatic brain metastases at initial diagnosis may be treated with chemotherapy alone at the discretion of the patient's treating physician. A 4 week disease stable interval as confirmed by MRI or CT brain w/ contrast (Table 7.4-2) is required after treatment of brain metastases before initiation of thoracic radiation therapy.
- Prophylactic Cranial Irradiation (PCI) is not allowed.
- Treatment initiation must be  $> 3$  weeks but  $\leq 8$  weeks from the last dose of chemotherapy for all participants.
- The screening phase either ends with confirmation of full eligibility and initiation of study treatment or with the confirmation that the participant is a screen failure.
- This study permits the re-enrollment of a participant that has discontinued the study as a pretreatment failure before enrollment. If re-enrolled, the participant must be reconsented. A new participant identification number will be assigned at the time of re-enrollment.

**2. Treatment:** The treatment phase begins with a study initiation call to the MCRN. Treatment is to begin within 3 business days of study initiation.

Study therapy is administered as described in Tables 5.2-1 and 6.5-1 until disease progression, discontinuation due to toxicity, withdrawal of consent, the study ends, or other criteria for discontinuation are met, as described in Section 4.6 and Section 6.5.3.4. Patients may be treated beyond initial progression as specified in Section 6.5.5.

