## 6.4 Method of Assigning Participant Identification

Every participant that signs the informed consent form must be assigned a participant number. The investigator or designee will register the participant for enrollment by following the enrollment procedures established by principle investigator.

All participants must be registered with the MCRN Coordinating Center to be able to participate in a trial. The participating site must fax or email the completed study specific eligibility checklist and registration forms, supporting documents and signed informed consent to the Coordinating Center. Unsigned or incomplete forms will be returned to the site. Once documents are received, the MCRN Research Coordinator will review them to confirm eligibility and to complete the registration process. If eligibility cannot be confirmed, the research coordinator will query the site for clarification or additional documents as needed. Participants failing to meet all study eligibility requirements will not be registered and will be unable to participate in the trial.

Upon completion of registration, the MCRN Research Coordinator will provide the participating site with the study sequence number, if indicated. Within 24-48 hours after registration, it is the site's responsibility to:

- Enter the demographic and on-study patient information into the Oncore database
- Order investigational agent(s) if indicated per protocol

It is the responsibility of the participating Investigator or designee to inform the participant of the research treatment plan and to conduct the study in compliance with the protocol as agreed upon with Moffitt Cancer Center and approved by the site's IRB.

To register a patient, the completed and signed eligibility checklist along with supporting documentation must be sent to the MCRN via email at [[contact]](mailto:[contact]) or via fax at [contact], Monday through Friday between 8:00AM and 5:00PM (EST).

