Attempt collection of tumor tissue for pathologic confirmation and exploratory biomarker evaluation	X	Although it is not required, a serious attempt must be made to obtain diagnostic tumor tissue for confirmation of small cell pathologic diagnosis and for exploratory endpoints. (FFPE) tumor tissue block or minimum of 10 slides, obtained from core biopsy, punch biopsy, excisional biopsy or surgical specimen). Fine needle aspiration is sufficient if that is the only available tissue. Archival tumor material must be made available.
Moffitt Cancer Research Network/Clinical Drug Supplies		
Phone calls to MCRN		Phone calls must be made to MCRN as follows:  Screening phone call to IVRS: For participant number assignment at the time informed consent is obtained.

A-Screening Procedure Visit cannot be more than 28 days before initiation of RT

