All known or suspected sites of disease (including CNS) should be assessed at screening and at subsequent assessments using the same imaging method and technique. If more than one method is used at screening, then the most accurate method according to RECIST 1.1 should be used when recording data and should again be used for all subsequent assessments. Bone scan, PET scan, and ultrasound are not adequate for assessment of RECIST 1.1 response. In selected circumstances where such modalities are the sole modality used to assess certain non-target organs, those non-target organs may be evaluated less frequently. For example, bone scans may need to be repeated only when complete response is identified in target disease or when progression in bone is suspected. Previously treated CNS metastases are not considered measurable lesions for purposes of RECIST 1.1 response. Screening assessments should be performed within 28 days of initiation of radiation therapy. Participants will be evaluated for tumor response outlined in Table 7.4-1 and Table 7.4-2 or more frequently as clinically indicated or per local Standard of Care, until disease progression (or until

discontinuation of study drug in participants receiving study therapy beyond progression), lost to follow-up, withdrawal of study consent, or the study ends. Tumor assessments for all participants should continue as per protocol even if dosing is delayed. Tumor measurements should be made by the same investigator or radiologist for each assessment whenever possible.

As outlined in section 9.4.1, progression free survival will be calculated from the date of patient registration. The baseline scan for RECIST 1.1 response evaluation will be the imaging assessment performed 2 weeks after completion of thoracic radiation and prior to C1D1 of combined ipilimumab/nivolumab. If the patient progresses between pre-treatment imaging and the baseline scan prior to initiation of ipilimumab/nivolumab, this will be considered disease progression according to the defined primary endpoint. In this circumstance, at the investigator's discretion, the patient may elect to receive study drugs beyond progression according to section 6.5.5. Tumor imaging assessments for ongoing study treatment decisions will be completed by the investigator using RECIST 1.1 criteria.

**Table 7.4-1.** Schedule of CT/MRI Tumor Assessments A

Time On Study	Assessment Frequency	Assessment Week (Day 1 of Week Shown)	Assessment Window

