Screening		Week 0	± 28 days
Baseline (RECIST 1.1)		Week 4 (prior to initiation of ipilimumab/nivolumab)	+/- 5 days
Between Week 10 and Week 35	Every 8-9 weeks after initiation of Nivolumab/Ipilimumab	10,19,27,35,	± 5 days
Beyond Week 35	Every 12 weeks	47,59,71+,	± 5 days

A-Acceptable Radiographic Tumor Assessments:

---CT/ Chest-With IV contrast preferred.

---CT/MRI Abdomen-With oral and IV contrast preferred.

---CT/MRI Pelvis-With oral and IV contrast preferred. Only required if patient has known pelvic visceral metastases or bony metastases in the pelvis.

**Table 7.4-2.** Schedule of MRI/CT Brain Surveillance Assessments A

Time On Study	Assessment Frequency	Assessment Week (Day 1 of Week Shown)	Assessment Window
Screening/Baseline		Week 0	Within 28 days
Week 10	Every 12-13	Weeks 10, 23, 35, 47,59+	±5 days

	weeks	
--	-------	--

A-MRI/CT Brain-with contrast if possible. MRI preferred.

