## 9.4 Endpoints

### 9.4.1 Primary Endpoints

**Part I: Safety Run In Phase I:** Unacceptable toxicity status at the end of 13-week safety observation period with unacceptable toxicity defined as:

- Any grade 4 immune related adverse event (irAE),
- Any  $\geq$  grade 3 noninfectious pneumonitis,
- 
- Any grade 3 irAE, excluding pneumonitis, that does not downgrade to grade 2 within 7 days after onset of the event despite optimal medical management including systemic corticosteroids or does not downgrade to  $\leq$  grade 1 or baseline within 14 days,
- Liver transaminase elevation  $> 8 \times$  ULN or total bilirubin  $> 5 \times$  ULN,
- Any  $\geq$  grade 3 non-irAE, except for the following exclusions:
  - grade 3 fatigue lasting  $\leq$  7 days
  - grade 3 endocrine disorder (thyroid, pituitary, and/or adrenal insufficiency) that is managed with or without systemic corticosteroid therapy and/or hormone replacement therapy and the participant is asymptomatic
  - grade 3 infusion-related reaction (first occurrence and in the absence of steroid prophylaxis) that resolves within 6 hours with appropriate clinical management
  - grade 3 or 4 neutropenia that is not associated with fever or systemic infection that improves by at least 1 grade within 3 days.

**Part II: Phase II:** The primary endpoint is 6-month PFS status. PFS is defined as the duration from date of registration to date of first documentation of progression assessed by local investigator or symptomatic deterioration (as defined above) or death due to any cause. Patients last known to be alive without report of progression are censored at date of last disease assessment. For patients with a missing scan (or consecutive missing scans) whose subsequent scan determines progression, the expected date of the first missing scan (as defined by the disease assessment schedule) will be used as the date of progression.

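### Six-month PFS is counted from registration but settled by a Week 27 CT timed from radiotherapy, and the go/no-go count says neither how to treat a scan after the mark nor what cut-off applies above 52 patients

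*Combined protocol and SAP*

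**What the plan says.** **Time origin.** Section 9.4.1: "PFS is defined as the duration from date of registration to date of first documentation of progression assessed by local investigator". Symptomatic deterioration and death also count as events. Section 7.4 repeats that "progression free survival will be calculated from the date of patient registration". Patients without progression are censored at their last disease assessment. The only back-dating rule covers scans that were missed.

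**Scan clock.** Section 4.2: "On-study tumor assessments commence 4 weeks after initiation of thoracic radiation therapy". Appendix 1 places the first radiotherapy fractions in W1. Table 7.4-1 puts body CTs at Weeks 10, 19, 27 and 35, each ±5 days, but its frequency column reads "Every 8-9 weeks after initiation of Nivolumab/Ipilimumab". The Week 23 scan in Table 7.4-2 is of the brain only.

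**Registration to radiotherapy.** Section 4.2.1 says "Treatment is to begin within 3 business days of study initiation", counted from the study initiation call. It also says "Screening begins after the participant signs the informed consent form (ICF) and is enrolled on the study", and Table 7.1-1 adds "Screening Procedure Visit cannot be more than 28 days before initiation of RT". Section 6.4 points to a later registration: "Participants failing to meet all study eligibility requirements will not be registered".

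**Decision.** Section 9.2 tests 24% against 44% with a Simon two-stage design: continue if at least 5 of 18 are free of progression at 6 months, and reject the null if at least 18 of 52 are. The total may rise to 57 to allow for censoring. The final PFS analysis is targeted for 6 months after the last enrolment. Section 9.5.2 estimates PFS by Kaplan-Meier, at that point and again at the OS analysis.

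No section gives 6 months in days, a window around the mark, or the scan that settles 6-month status.

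**The concern.** Progression is dated when it is first documented, and around the mark the scheduled body CT does most of the documenting. The scan and the endpoint run on different clocks. A site that follows the plan exactly can therefore find progression on an on-time Week 27 CT, date it after 6 months, and have the patient counted as not progressed. Two patients with the same disease course can be classified differently because of the gap before radiotherapy or the day chosen within the scan window.

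The counts at stake decide whether the regimen goes to a phase III trial. Two related gaps affect the same counts: the analysis may be taken before the last Week 27 scans are due, and the permitted extra patients have no rejection cut-off.

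**Working it through.** **1. The plan's own design.** With n patients in total and final cut-off c, P(reject) = Σ over x = 5 to 18 of Bin(18, x; p) × P[Bin(n − 18, p) ≥ c − x]. For n = 52 and c = 18 this gives type I error 0.049 at p = 0.24 and power 0.903 at p = 0.44. Section 9.2 reproduces.

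**2. Where the Week 27 CT falls.** Six months is taken as 365.25/2 = 182.6 days. The plan supports two readings of the week number:

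| Reading | Week 27 Day 1 | Window in days from radiotherapy start |
|---|---|---|
| Week 1 Day 1 is radiotherapy start (Appendix 1) | 26 × 7 = 182 | 177 to 187 |
| Week n means n weeks after radiotherapy start (Section 4.2 wording) | 27 × 7 = 189 | 184 to 194 |

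Days from registration are these plus the registration-to-radiotherapy lag. On the first reading the window straddles the mark at zero lag and lies wholly after it once 177 + lag exceeds 182.6, that is, from a lag of 6 days. If scans are spread evenly over the window, the share after the mark is (187 + lag − 182.6)/10: 0.44 at zero lag, 0.74 at 3 days, 0.94 at 5 days. On the second reading the window follows the mark even at zero lag. An anchor at the first drug dose, as the frequency column suggests, would add the variation in when the drugs start.

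**3. How many patients are exposed.** Assume exponential PFS at the null: hazard = −ln(0.24)/182.6 = 0.0078 per day. The expected number progressing between the Week 19 CT (day 126 or 133) and 6 months is 52 × [exp(−hazard × (Week 19 day + lag)) − 0.24]. On the first reading this is 6.9 at zero lag, 6.2 at 5 days and 3.1 at 28 days; on the second, 5.9, 5.2 and 2.3. Under that assumption these are ceilings on misclassification, because some of these patients will be found earlier by other means.

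**4. Analysis date.** At 4 patients per month (Section 9.2.1), taking enrolment as registration, the number whose window is still open 6 months after the last enrolment is 4 × (187 + lag − 182.6)/30.4: 1.0 at a lag of 3 days and 1.5 at 7 days. Only patients still event-free need the scan. Multiplying by 0.24 to 0.44 leaves about 0.2 to 0.7 of a patient. With 194 in place of 187 the range is about 0.5 to 1.1.

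**5. More than 52 patients.** The formula in step 1, with stage 1 unchanged and all patients evaluable:

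| n | Type I error at ≥18 | Cut-off keeping it ≤0.05 | Type I error | Power |
|---|---|---|---|---|
| 53 | 0.058 | ≥19 | 0.032 | 0.882 |
| 54 | 0.067 | ≥19 | 0.038 | 0.896 |
| 55 | 0.077 | ≥19 | 0.045 | 0.908 |
| 56 | 0.087 | ≥20 | 0.030 | 0.888 |
| 57 | 0.098 | ≥20 | 0.035 | 0.901 |

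**6. Price of counting Week 27 progression as failure.** Put p = 0.24 and p = 0.44, each raised to the power (scan day + lag)/182.6, through the unchanged ≥5/18 and ≥18/52 rule:

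| Lag (days) | Day 182: type I error, power | Day 189: type I error, power |
|---|---|---|
| 3 | 0.042, 0.893 | 0.026, 0.857 |
| 5 | 0.037, 0.884 | 0.022, 0.846 |
| 7 | 0.032, 0.873 | 0.019, 0.834 |
| 14 | 0.019, 0.834 | 0.011, 0.788 |
| 28 | 0.006, 0.736 | 0.003, 0.679 |

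These take every scan on its nominal day. If every scan fell on the last day of its window (187 or 194), power at lags of 3 to 7 days would be 0.87 to 0.85 and 0.83 to 0.80.

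**The case against.** Kaplan-Meier is the stated method for the PFS analyses. It handles censoring, and the 6-month rate is re-estimated a year after the last enrolment, by which time the Week 27 windows have closed. The analysis date is only a target. Section 6.4 implies that screening is finished before registration, so the lag is probably short, and 28 days sits poorly with it. Deaths, symptomatic deterioration, clinically indicated scans and the Week 23 brain scan will catch some progressions before the mark. The extra patients are meant to allow for censored ones, so 57 evaluable patients is not the intended case.

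Much of this stands, and it limits the size of the problem. It does not remove it. The decision rule in Section 9.2 counts patients, and the Kaplan-Meier estimate gives no status in that count to a patient last scanned at Week 19. A short lag does not help much: at 5 days, 94% of the window is late on the first reading and all of it on the second. The 3 business days run from the initiation call, which is not stated to be registration. Nothing says how many of the extra patients must be censored for a cut-off of 18 to remain valid.

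A reader might go further and infer that the true type I error is well above 5%. Put an apparent rate of 0.24 + (1 − share caught earlier) × (share of window after the mark) × (PFS at Week 19 − 0.24) through the rule. With exponential PFS, a benchmark free of scan delay and 50% to 90% caught earlier, the result is 0.06 to 0.24 over lags of 0 to 28 days. The documents supply none of those inputs. If the 24% benchmark carried the same delay, the bias would cancel.

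**Conclusion.** The point holds as a gap in definition with a known direction. As written, progression first seen on an on-time Week 27 CT can be counted as success, which favours a positive result. That the window straddles or follows the mark rests only on the plan's own dates, under either reading of the week number. The size of any inflation cannot be settled, because the lag, the share caught earlier, and the benchmark's scan schedule and time origin are not given.

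The effect of the analysis date is small at short lags, around one event-free patient or fewer, and larger if registration comes early. The cut-off gap above 52 needs no assumption about scan timing: with all patients evaluable and 18 retained, type I error runs from 0.058 at 53 to 0.098 at 57.

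A reader might also conclude that the endpoint should be moved wholesale to a landmark counted from radiotherapy. The documents do not support that. Measured from registration, such a landmark would still vary with each patient's lag, and step 6 of the working shows what long lags cost in power. The sample size itself is sound.

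**What to change.** 1. In Sections 9.2 and 9.4.1, define 6 months as a fixed number of days from registration. State that progression first documented on the on-time Week 27 CT (±5 days) counts as failure for 6-month status at both Simon stages. Say how a patient without an evaluable Week 27 assessment is counted, for example as a failure.
2. Take the stage 1 and final PFS counts only after the Week 27 window of the last relevant patient has closed.
3. Give the final cut-off if more than 52 patients are evaluable. With stage 1 at ≥5/18, ≥19 for 53 to 55 and ≥20 for 56 or 57 keep type I error at or below 0.05, with power 0.88 to 0.91.
4. Reconcile the scan anchor across Section 4.2, Appendix 1 and Table 7.4-1. Require registration close to radiotherapy start, or state the expected lag, and restate type I error and power for it.
5. Keep the registration-based Kaplan-Meier estimate and add an interval-censored sensitivity analysis.

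No scans are added. Decisions come about 1 to 5 weeks later, depending on lag and week numbering, and the 6-month rate reads slightly lower. With ≥18/52 kept and lags of 3 to 7 days, power on nominal scan days is about 0.87 to 0.89 (day 182) or 0.83 to 0.86 (day 189), with type I error below 0.05. The loss grows with the lag, which is why item 4 belongs with item 1.

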Additionally, patients who have progressed between screening imaging and baseline imaging (See Table 7.4-1) but prior to initiation of ipilimumab/nivolumab may be allowed to proceed with ipilimumab/nivolumab beyond progression at the investigator's discretion. All decisions to continue treatment beyond initial progression must be discussed with the Principal Investigator and documented in the study records. The participant will continue to receive monitoring according to the Time and Events Schedules in Table 7.1-2 and Table 7.1-3. A radiographic assessment should be performed within 6 weeks of original PD to determine whether there has been a decrease in the tumor size, or continued PD. For the participants who continue study therapy beyond PD, further progression is defined as an additional 10% increase in tumor burden from time of initial PD. This includes an increase in the sum of all target lesions and/or the development of new measurable lesions. For patients with evaluable disease only, further progression is defined as unequivocal disease progression of non-target lesions or the development of new lesions from time of initial PD. Treatment should be discontinued permanently upon documentation of further disease progression. New lesions are considered measurable at the time of initial progression if the longest diameter is at least 10 mm (except for pathological lymph nodes, which must have a short axis of at least 15 mm). Any new lesion considered non-measurable at the time of initial progression may become measurable and therefore included in the tumor burden measurement if the longest diameter increases to at least 10 mm (except for pathological lymph nodes, which must have an increase in short axis to at least 15 mm).

For statistical analyses that include the investigator-assessed progression date, participants who continue treatment beyond initial investigator-assessed, RECIST 1.1-defined progression will be considered to have investigator-assessed progressive disease at the time of the initial progression event. For participants in all treatment arms, global deterioration of health status requiring discontinuation of treatment without objective evidence of disease progression at that time should be reported as 'symptomatic deterioration'. Every effort should be made to document objective progression (i.e., radiographic confirmation) even after discontinuation of treatment.

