## 9.2 Phase I/II Sample Size Determination

We propose a single arm, non-randomized phase I/II study, with the goal to evaluate efficacy compared to historical controls. Slotman et al. [5] reported a 6-month progression-free survival (PFS) of 24% with platinum-based chemotherapy and thoracic radiation therapy. We would propose to pursue a phase III randomized controlled study if there is a 20% improvement in 6-month PFS with the addition of combined immune checkpoint blockade as part of the proposed clinical study. Therefore, this regimen would be considered not worthwhile to pursue if the true 6-month PFS is 24% or less and worth pursuing if the true 6-month PFS is 44% or greater. The trial will use a Simon's 2-stage design[49] with 1-sided 0.05 level type I error and 90% power. The total target sample size is 52 patients. During the 1st stage, 18 patients will be accrued. If 4 or fewer patients have not progressed at 6 months, the study will be closed for futility. However, if at least 5 patients have not progressed at 6 months, then the study will continue to accrue an additional 34 patients. Once the total number of patients has accrued (n=52), then the null hypothesis will be rejected if at least 18 patients have not progressed at 6 months. In order to accommodate censoring, we may increase the total sample size by up to 10% (n=57).

- The final PFS analysis is targeted to occur 6 months after the last participant is enrolled
- The final OS analysis is targeted to occur 1 year after the last participant is enrolled.

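### The missing-scan rule backdates a progression found after missed scans but not a death, so a patient unscanned at Weeks 19 and 27 who dies after 6 months counts as a 6-month PFS success

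*Combined protocol and SAP*

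**What the plan says.** Section 9.4.1 states: "The primary endpoint is 6-month PFS status". The time-to-event definition behind it reads: "PFS is defined as the duration from date of registration to date of first documentation of progression assessed by local investigator or symptomatic deterioration" "or death due to any cause". Two further provisions deal with incomplete follow-up:

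- Censoring: "Patients last known to be alive without report of progression are censored at date of last disease assessment".
- Missed scans: "For patients with a missing scan (or consecutive missing scans) whose subsequent scan determines progression, the expected date of the first missing scan", taken from the assessment schedule, becomes the progression date.

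Section 6.5.5 describes symptomatic deterioration as "global deterioration of health status requiring discontinuation of treatment without objective evidence of disease progression".

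Section 9.2 turns the endpoint into a count. The trial stops for futility with 4 or fewer successes among the first 18 patients. Among 52, "the null hypothesis will be rejected if at least 18 patients have not progressed at 6 months". Section 9.5.2 adds Kaplan-Meier estimates of PFS at 6 and 12 months.

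Table 7.4-1 schedules body scans at Weeks 10, 19, 27 and 35 (Day 1 of the week, ±5 days). I found no rule in sections 7.4, 9.2, 9.4 or 9.5 for the date of a death after missed scans, or for the status of a patient with no scan at 6 months.

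**The concern.** Backdating assumes that when scans are missed and progression is found later, the progression may have occurred earlier, unseen. That reasoning applies at least as well when the next thing known about the patient is death. Section 1.1.1 describes rapid progression after chemotherapy, with a median PFS of 2 to 3 months. Yet the rule requires a later scan, and the censoring sentence covers only living patients. A death after missed scans falls outside both and stays at its own date.

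The effect on the 6-month count can only be upward: a patient who may have progressed unseen before 6 months is scored as event-free. Section 9.2 ties the case for a phase III trial to this count, and 17 versus 18 of 52 decides it. The same patient also stays at risk and event-free at 6 months in the Kaplan-Meier estimate.

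**Working it through.** **1. Dating.** Day 1 of Week w falls 7(w − 1) days after the start of radiotherapy; one month is taken as 30.4375 days, so 6 months is 182.6 days.

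- Week 10: 63 days, 2.07 months
- Week 19: 126 days, 4.14 months
- Week 27: 182 days, 5.98 months
- Week 35: 238 days, 7.82 months

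The PFS clock starts at registration. The documents do not fix the gap to radiotherapy, so I assume 0 to 28 days. Week 19 then falls 126 to 154 days after registration (4.1 to 5.1 months), and Week 27 falls 182 to 210 days after it (6.0 to 6.9 months).

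**2. Same missed scans, different endings.** The patient is clean at Week 10, misses Weeks 19 and 27, and has no recorded symptomatic deterioration.

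| What happens next | Date under 9.4.1 | 6-month status |
|---|---|---|
| Progression on the Week 35 scan | Week 19 (4.1 to 5.1 months) | Failure |
| Death at 7.5 months, no scan in between | 7.5 months | Success |
| Alive, never scanned again | Censored at Week 10 | Not stated for the Simon count |

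**3. If only Week 27 is missed.** A progression on the Week 35 scan goes back to Week 27. That is 0.6 of a day short of 6 months with no registration gap, and past 6 months with a gap of one day or more. It usually counts as a success, as does a death at 7.5 months. The two endings are therefore scored differently mainly when Week 19 is missed as well.

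**4. The plan's own design.** From section 9.2: n1 = 18, continue with at least 5; N = 52, reject with at least c = 18; null rate 0.24, alternative 0.44, one-sided 0.05, power 90%.

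P(reject | p) = Σ over x = 5 to 18 of C(18, x) pˣ (1 − p)¹⁸⁻ˣ × P[Bin(34, p) ≥ c − x]

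- p = 0.24: 0.0494
- p = 0.44: 0.9035

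The stated design is reproduced.

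**5. Sensitivity by number of patients.** Suppose k true failures are scored as successes in the final count and none affects stage 1. Reaching 18 then needs only 18 − k true successes. With p = 0.24:

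| k | True successes needed | Type I error |
|---|---|---|
| 0 | 18 | 0.049 |
| 1 | 17 | 0.084 |
| 2 | 16 | 0.132 |
| 3 | 15 | 0.190 |

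**6. Sensitivity by fraction.** Suppose a fraction f of true failures is scored as success in both stages. The apparent rate is 0.24 + 0.76f, and the expected number among 52 is 52 × 0.76 × f.

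| f | Apparent rate | Expected patients | Type I error |
|---|---|---|---|
| 1% | 0.248 | 0.4 | 0.064 |
| 2% | 0.255 | 0.8 | 0.082 |
| 3% | 0.263 | 1.2 | 0.103 |
| 5% | 0.278 | 2.0 | 0.155 |
| 10% | 0.316 | 4.0 | 0.337 |

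These errors are somewhat larger than in step 5 for a similar number of patients, because misclassified patients also help the trial past the stage 1 stop. Both k and f are assumptions; the documents give no rate of death after missed scans.

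**The case against.** The strongest reply is that very few patients can be affected. Deterioration that forces a patient off treatment is already a PFS event without a scan. Section 4.2.1 keeps patients who stop for reasons other than progression on the imaging schedule, and sections 6.5.3.4 and 7.4 continue scans through interruptions and delays. Section 6.5.5 asks for every effort to document progression after stopping, and Table 7.4-2 adds a brain scan at Week 23. A misclassified patient must miss Weeks 19 and 27, progress unseen before 6 months, survive past 6 months and die without another scan. This stands, and it limits the likely size. It does not close the gap: the deterioration wording requires stopping treatment, so it does not clearly reach a patient already off drug, and a scheduled scan can still be missed.

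A second reply is that dating a death at death is a legitimate convention. Moving every death back to the first missed scan would turn an unrelated death at 7.5 months into an event at about month 4, when the patient was known to be alive. That also stands, and is a reason not to make such backdating the primary rule.

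Several stronger readings are tempting but unsupported:

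- That any patient unscanned near 6 months who later dies is scored differently from one with later progression. Step 3 shows this is mainly untrue when only Week 27 is missed.
- That the 11% stopping for treatment-related events in section 1.1.3 (0.11 × 52 = 5.7, about 6 patients) measures exposure. It is a rate of stopping drug in recurrent disease, not of missing scans.
- That section 9.2, by speaking of patients who have not progressed, counts any death without documented progression as a success. The endpoint is PFS status and section 9.4.1 makes death an event, so a death before 6 months is a failure.
- That the comparison with the historical 24% is shown to be biased. The documents do not say how that figure treated deaths after missed scans.

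**Conclusion.** The asymmetry is real on the text of section 9.4.1, and nothing I found elsewhere removes it. It changes 6-month status mainly for a patient with no assessment from Week 19 through Week 27, no recorded symptomatic deterioration, and a death after 6 months without a scan in between.

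The number of such patients is probably small and cannot be estimated from the documents. The decision rule has little room for them: under the assumptions of step 5, a single one takes the type I error above the stated 5%. These figures show how sensitive the rule is; they do not predict the trial's error rate.

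This should be fixed because it concerns the primary go/no-go count and the error runs in one direction. Confidence is moderate.

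**What to change.** In sections 9.2 and 9.4.1, define a success for the Simon count as a patient alive and progression-free at 6 months, shown by a disease assessment without progression at or after the scheduled Week 27 visit (with its ±5-day window). State that a patient who dies after 6 months without such an assessment, having missed the scheduled scans before death, is not a success. The same definition settles the case where only Week 27 is missed and the status of living patients with no 6-month scan.

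For the Kaplan-Meier analysis, keep the date of death as the event date. Add a sensitivity analysis that dates deaths after missed scans by the missing-scan rule used for progression. Say in section 9.5.2 that the Simon count and the Kaplan-Meier estimate may differ for these patients.

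The cost is a few sentences, settled before outcomes are reviewed, and no new data. The 6-month figure may be slightly less favourable. Because the historical 24% may rest on another convention, report the 6-month result both with the scan requirement and with deaths kept at their own date.
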